#### **2.4. Overall study design**

Both trials (“short-stay” and “same-day” surgery cohorts) will test the same hypothesis, and have the same protocol aims, inclusion and exclusion criteria, procedures, assessments, methods of data analysis, and hypothesis testing, but are otherwise separate (and separately analyzed). Two cohorts are studied because their operations may have different pain intensities and opioid requirements. The protocol is very similar (hypothesis, aims, inclusion/exclusion, procedures, assessments, data analysis, hypothesis testing) to that of the dose-finding Pilot (Preliminary Studies). In each cohort, patients will be randomized to general anesthesia with methadone or short-duration opioids. Patients are followed in-hospital, then queried daily for 30d after discharge through emailed REDCap or paper surveys. Additional REDCap surveys will be emailed at 6 and 12mo.

Target enrollment is 300 evaluable subjects per cohort (150 control, 150 methadone). A 25% overall drop-out rate prior to 30d follow-up is conservatively assumed, thus 375 subjects in each cohort will be studied (750 total).

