## 1. SYNOPSIS

Study Title	Optimizing outpatient anesthesia
Objective	
In separate cohorts of patients undergoing moderately painful outpatient surgery (“short-stay” requiring overnight hospitalization with intended next day discharge and “same-day” surgery), compare the influence of general anesthesia with long-duration vs short-duration opioids on
 
 
1. short-term (before discharge) and intermediate term (1-30d post-discharge) opioid consumption.
 
2. short-term (immediate postoperative), intermediate term (1-30d post-discharge), and chronic (6 and 12 mo) postoperative pain.
 
3. short-term (immediate postoperative), intermediate term (1-30d post-discharge) opioid-related side effects
 
4. intermediate (30d post-discharge), and long-term (6 and 12 mo) quality of recovery.
 

Study Period	
Approximately 30 days per subject, plus 6 and 12 month follow-up  Total enrollment duration: Approximately 4 years

Number of Patients	
600 evaluable subjects. Estimated number to be studied is 750 with 25% loss to follow-up.  Estimated enrollment is 1000 to account for schedule changes, withdrawals, etc.

Inclusion and Exclusion Criteria	
Inclusion Criteria
 
 
1. Age 18-65 years
 
2. Undergoing general anesthesia and moderately painful ambulatory surgery with anticipated postop stay of < 24 hours
 
3. Signed, written, informed consent
 
 
Exclusion Criteria
 
 
1. History of liver or kidney disease.
 
2. Females who are pregnant or nursing.
 
3. Chronic opioid use (e.g. preoperative daily use of methadone, buprenorphine, fentanyl transdermal patches, or <math>\geq 3</math> oxycodone pills)
 

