Study Design	
Single-center, randomized, double blinded, parallel-group, 2-cohort investigation. Patients receive standard monitoring for anesthesia and postoperative care. Surgical and anesthesia care (except for intraoperative opioid use) are not altered for study purposes. In each cohort, subjects are randomized 1:1 to either long-duration opioid (IV methadone HCl) or typical short-duration opioid (IV e.g. fentanyl, morphine or hydromorphone at anesthesia provider discretion) intraoperatively and postoperatively in the recovery room. Intraoperative methadone doses are 15 mg in “short-stay” patients (10 mg if <math>\leq 55</math>kg) and 10 mg in “same-day” surgery patients.

Study Drug Administration	
In each of two cohorts (“short-stay” and “same-day” outpatients), 375 patients are randomized 1:1 (187 each) to receive long-duration opioid (IV methadone HCl) or typical short-duration opioid (e.g. fentanyl, morphine or hydromorphone at anesthesia provider discretion) intraoperatively & postoperatively in the recovery room (PACU).

Measurements	
Patients complete a questionnaire about current pain, past 7 day average pain, pain interference with activities of daily living, and expected level of postoperative pain. Total intraoperative and postoperative opioid administration during hospitalization will be recorded from the medical record. Pain intensity will be assessed using a verbal Numeric Rating Scale (NRS). Pain relief will be assessed using five point scale (0-no relief, 4-complete pain relief). Postoperative sedation will be recorded using Modified Observer’s Assessment of Alertness/Sedation (MOAA/S). Opioid-related side effects will be assessed using the Opioid-Related Symptom Distress Scale (ORSDS). Daily opioid consumption and pain self-assessments using a NRS and ORSDS will be recorded for approximately 30

	
days after surgery using anemailed REDCap or paper survey tool. Pain (PROMIS Pain Intensity and Pain Interference) and recovery (patient-reported quality of life, functional independence, health status, ability to return to work and normal activities; PROMIS global health, PROMIS-29, Veterans RAND 12-item VR-12 survey, Barthel index of activities of daily living, Quality of Recovery QoR-15) will be assessed at 7d, 14d, 21d, 30d, 6mo and/or 1yr postoperatively. Blood will be collected for future DNA analysis (CYP2B6 or pain-related genes).

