### 2.7 Sample size justification

Sample size is based on the primary outcome measure, total 30d post-discharge home opioid use (number of opioid tablets). Based on available reports (Background) and the Preliminary Results, an ideal state of post-discharge opioid use is defined as  $\leq 5$  pills in 30 days. In the Preliminary data, the rate of "high" post-discharge opioid use (defined as  $> 5$  pills in 30d) was 45% in the short-duration opioid group. With a conservative assumption of a relative risk of 65% for the long-duration group (30% rate of "high" opioid use), a total of 300 subjects (150 per group) will be needed to achieve 80% power assuming alpha = 0.05.

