### **3.0 Recruitment strategy and feasibility**

Subjects will be 18-65 yr. Because this is the first evaluation of methadone for outpatient anesthesia, children and older patients will not be studied (because of declining methadone elimination and increased risk of respiratory depression with age). Such studies may ensue after safety is established in the present investigation. Sample size calculations show that 300 evaluable (completing 30d follow-up) patients are needed in each of the 2 study cohorts (600 total). Change in scheduled operation, prolonged ( $>1$ d) stay of scheduled short-stay (next day discharge) patients, unanticipated admission of same-day patients, or patient withdrawal has occurred in  $\sim 10\%$  of our study patients to date. This, combined with post-op loss to follow-up (see below), suggests a potential overall drop-out rate before completion of 30d follow-up of  $<15\%$ . Hence, to ensure 300 pts evaluable at 30d, a conservative 25% drop-out is estimated and 375 pts in each of the 2 study cohorts will be randomized (750 total). The Duke Department of Anesthesiology provides anesthetics for  $>66,000$  procedures per year. The main campus of Duke University Health System includes Duke University Hospital which is a 957 bed facility. In 2016 there were 41,408 patients admitted and 1,119,151 outpatient visits. Duke University Hospital includes the Duke North Hospital/Duke Medical Pavilion ( $\sim 54$  ORs), the Children’s Health Center, the Duke Eye Center (6 ORs), and Ambulatory Surgery Center (9 ORs). Between the Duke North Hospital/Duke Medical Pavilion and Ambulatory Surgery Center there were 34,492 anesthetics performed in 2017. These included, for example, 375 laparoscopic cholecystectomies and 269 laparoscopic hysterectomies  $\pm$  salpingoophorectomies, further supporting specific feasibility. If enrollment lags, or for strategic advantage, Duke Regional and/or Duke Raleigh Hospitals can be added as future sites.

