#### **4.2 Premature Discontinuation**

If a subject withdraws from the study before the administration of study drug, or there is a protocol violation, the subject will be replaced in order to provide the required number of subjects. Dropouts and withdrawals (after study drug administration) will not be replaced, in case this is not random but outcome-related. Subjects will be withdrawn if the investigator decides that discontinuation is in the best interest of the subject, or the subject requests withdrawal from the study.

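### 375 patients per cohort give 300 evaluable only up to 20% drop-out; at the stated 25% they give about 281

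*Combined protocol and SAP*

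**What the plan says.** Section 2.4 sets a target of 300 evaluable subjects per cohort, 150 per arm, and continues: "A 25% overall drop-out rate prior to 30d follow-up is conservatively assumed, thus 375 subjects in each cohort will be studied (750 total").

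The same pairing appears in two other places:

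- Synopsis, Number of Patients: "600 evaluable subjects. Estimated number to be studied is 750 with 25% loss to follow-up". The next sentence adds a larger figure: "Estimated enrollment is 1000 to account for schedule changes, withdrawals, etc".
- Section 3.0: "to ensure 300 pts evaluable at 30d, a conservative 25% drop-out is estimated and 375 pts in each" of the two cohorts are to be randomised. The sentence before it says that experience to date "suggests a potential overall drop-out rate before completion of 30d follow-up of" less than 15%. Section 3.0 also defines evaluable as completing the 30-day follow-up.

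The Synopsis (Study Drug Administration) gives the split by arm: "375 patients are randomized 1:1 (187 each) to receive long-duration opioid" or the short-duration comparator.

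On replacement, Section 4.2 says: "Dropouts and withdrawals (after study drug administration) will not be replaced, in case this is not random but outcome-related". The sentence before that does provide for replacing subjects who withdraw before study drug or who have a protocol violation.

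The base size is in Section 2.7: 45% high opioid use (more than 5 pills in 30 days) in the control group, 150 per group, 80% power, alpha 0.05. The effect is introduced with the words "With a conservative assumption of a relative risk of 65% for the long-duration group (30% rate of" high use).

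**The concern.** To finish with 300 patients after losing a fraction *d* of those studied, one must start with 300/(1 − *d*). The protocol appears to have used 300 × (1 + *d*), which always gives too few. At 25% the two formulas differ by 25 patients per cohort, which is too much for rounding.

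The protocol presents 25% as its conservative case and says that 375 will secure 300 evaluable patients under it. If that is untrue, the cushion is thinner than a reader of the plan would believe. Because the cohorts are analysed separately, each carries the shortfall by itself. The 80% power in Section 2.7 is tied to 300 evaluable, so it too would not hold in the case the plan claims to cover.

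**Working it through.** **Inputs.** Evaluable target 300 per cohort, 150 per arm (Section 2.4). Drop-out 25%, with 375 per cohort and 750 in total (Synopsis, Sections 2.4 and 3.0). Arm size 187 (Synopsis). Expected drop-out below 15% (Section 3.0). Control rate 45%, relative risk 0.65, 80% power, alpha 0.05 (Section 2.7). Section 2.7 does not say whether alpha is two-sided; I assume that it is.

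**Step 1. Reproduce 375.**
- 300 × (1 + 0.25) = 375. This is the plan's figure exactly.
- 300 / (1 − 0.25) = 400. This is the number that a 25% loss requires.
- 1 − 300/375 = 0.20. This is the loss that 375 covers.

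**Step 2. Evaluable patients left.**

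| Drop-out | Per cohort, from 375 | Both cohorts, from 750 |
|---|---|---|
| 15% | 318.75 | 637.5 |
| 20% | 300 | 600 |
| 25% | 281.25 | 562.5 |

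At 25% the shortfall is 300 − 281.25 = 18.75 per cohort, or 37.5 overall. Per arm, 187 × 0.75 = 140.25 against the planned 150.

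**Step 3. Reproduce the base sample size.** The rate implied by the relative risk is 0.65 × 0.45 = 0.2925. For a two-proportion test with pooled variance under the null and no continuity correction:

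n per group = [z(0.975) √(2 p̄(1 − p̄)) + z(0.80) √(p₁(1 − p₁) + p₂(1 − p₂))]² / (p₁ − p₂)²

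Here p₁ = 0.45, p₂ = 0.2925 and p̄ = 0.37125. The two square roots are 0.6833 and 0.6741, and the difference is 0.1575.

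n = [(1.960 × 0.6833 + 0.8416 × 0.6741) / 0.1575]² = 146.5, so 147 per group (294 in total). This agrees with the plan's 150.

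**Step 4. Power at each drop-out rate.** Power = Φ{[0.1575 √n − 1.960 × 0.6833] / 0.6741}, with n the evaluable number per arm.

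| Drop-out | n per arm | Power |
|---|---|---|
| 15% | 159.4 | 83.2% |
| 20% | 150 | 80.9% |
| 25% | 140.6 | 78.3% |

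Exact enumeration of the uncorrected chi-square test gives nearly the same values: 83.1% (160 + 159), 80.9% (150 + 150) and 78.1% (141 + 140). Power stays at or above 80% until evaluable numbers fall below 294, which is a loss of 1 − 294/375 = 21.6%.

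**Sensitivity to the printed 30%.** Section 2.7 pairs a relative risk of 65% with a 30% rate, although 0.65 × 45% is 29.25%; a rate of 30% is a relative risk of 0.30/0.45 = 0.667. This is a separate point from the drop-out error, but it affects how much margin exists. With p₂ = 0.30 the same formulas require 163 per group. They give power of 76.8% at 150 per arm, 79.3% at 15% loss and 74.1% at 25% loss. Power of 80% would then hold only up to a loss of 1 − 326/375 = 13.1%.

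**The case against.** The best counter-argument is that other provisions may absorb the gap.

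- **Replacement.** Section 4.2 replaces subjects who withdraw before study drug or have a protocol violation. Section 3.0 counts changed operations and withdrawals within its overall drop-out. If replaceable events made up 5 of the 25 points, 375 treated patients would still give 300. That is possible, but the documents give no such split, the Synopsis calls the 25% loss to follow-up, and the derivation of 375 takes no credit for replacement.
- **The 1000 enrolled.** It covers schedule changes and withdrawals, which overlap with the events listed in Section 3.0, so the plan may be allowing for some of them twice. Even so, the Synopsis applies the 25% to the 750, and Section 3.0 says that 375 per cohort are randomised.
- **Partial data.** Section 2.8 says the analysis will not be restricted to completers and that the pill outcome will be analysed with and without drop-outs. Some drop-outs will have usable pill data, so the 78% is a worst case in which they contribute nothing. This stands as a qualification. However, Section 2.8 gives no rule for classifying a drop-out as above or below 5 pills, so full recovery of the lost information cannot be assumed.
- **Small consequence.** The target is met at the expected drop-out, and 25% loss costs about 2.6 points of power (80.9% − 78.3%). This is true, and it limits the weight of the point. It does not make the stated allowance correct.

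**Conclusion.** The concern holds. A 25% drop-out, 375 per cohort and 300 evaluable cannot all be true: 375 leaves 281 at 25%, and leaves 300 at 20%. The shortfall in the plan's own conservative case is about 19 patients per cohort (about 38 overall), and power there is about 78% instead of 80%. The power figures rest on a two-sided alpha of 0.05, 45% against 29.25%, an uncorrected test, and no information from drop-outs.

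The trial is not underpowered under what it expects at the planned relative risk. With less than 15% lost, at least 318 per cohort remain and power is about 83% or more. What is wrong is a stated property of the sample size, repeated in three places and applying to both cohorts. It should be corrected.

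**What to change.** Keep 375 per cohort and 750 in total, and change the drop-out allowance from 25% to 20% in the Synopsis (Number of Patients), Section 2.4 and Section 3.0. It remains above the expected rate of below 15%. The change is to wording only and needs no extra patients. The stated margin over the expected rate falls from 10 points to 5, but 5 is all that 375 ever provided.

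If the 25% is to stay, the plan should instead state that it leaves about 281 evaluable per cohort with about 78% power. Keeping both 25% and 300 would mean 400 per cohort, 50 more patients overall, which the expected drop-out does not call for.

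In the same edit, tidy Section 2.7. Either print 29.25% beside the relative risk of 65%, or keep 30% and state about 77% power at 150 per group. Say also that alpha is two-sided, if that is the intention.

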#### **2.5. Patient Selection**

Patients undergoing outpatient surgery at Duke University Hospital and Ambulatory Surgery Center will be recruited. Selection criteria are the same for both “short-stay” and “same-day” cohorts. If enrollment lags, or for strategic advantage, we will add Duke Regional or Duke Raleigh Hospitals, **at which point we will amend the protocol**. Sex and minority composition will approximate that of the greater Duke patient population, depending on the surgical cases available.

##### *Inclusion Criteria*

- Age 18-65 years
- Undergoing general anesthesia and moderately painful, ambulatory surgical procedures with anticipated postop hospital stay of < 24 hours
- Signed, written, informed consent

##### *Exclusion Criteria*

- History of or known liver or kidney disease
- Females who are pregnant or nursing
- Chronic opioid use (e.g. preoperative daily use of methadone, buprenorphine, fentanyl transdermal patches, or ≥ 3 oxycodone pills)

Patients will be approached prior to surgery in the Center for Preoperative Assessment and Planning or identified through IRB-approved review of the surgical schedule prior to their surgery, at which time they will be contacted and asked if they are interested in participating. An IRB-approved phone screen may be conducted and a consent visit scheduled in advance of surgery for subjects that wish to participate. This visit may also occur on day of surgery, allowing sufficient time for explanations, questions and answers. If interested and willing, subjects might also be fully consented using IRB approved electronic Informed Consent Form (eICF). All enrolled subjects must provide informed consent, evidenced by signing an informed consent document. They will be consented for participation and enrolled by trained study staff.

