### 2.6.3 Preoperative

Patients will complete a questionnaire about current pain, past 7 day average pain, pain interference with activities of daily living, and expected level of postoperative pain (NIH PROMIS-29 Profile v2.0, PROMIS Global Health Scale 1.2, <http://www.nihpromis.org/>). Quality of life indices will be assessed using the Veterans RAND 12-item health survey (VR-12), the Barthel index of activities of daily living, and the Quality of Recovery QoR-15. Demographic data will be recorded. Additional questions will query patients' current employment, level of normal activities, and expectation of time to return to work and normal activities. Demographic data including patient zip codes, employment status, education status, will be recorded. Patient information (demographics, medical history, procedure, medications, pain scores) will be extracted from patient's electronic medical records.

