Postoperative opioid use will be quantified from the medication monitoring system, patients' daily questionnaire, and residual pill counts, and recorded both as the number of tablets used and total morphine equivalents using standard opioid conversion tables.

Recovery from surgery/anesthesia will be assessed at 7d, 14d, 21d, 30d, 6mo and/or 1yr postoperatively, by assessing patient-reported quality of life, functional independence, health status, and ability to return to work and normal activities. We will assess quality of life (Veterans RAND 12-item health survey VR-12, functional independence (Barthel index of activities of daily living, recovery (QoR-15). QoR-15 assesses 5 domains of patient-reported health status: pain, physical comfort, physical independence, psychological support and emotional state using an 11-point numerical rating scale with results summed from 0 (poor recovery) to a maximum of 150 (excellent recovery). These are among the most commonly used instruments, are extensively validated and normed, and are our hospital standards, used locally for several years. Thus we can compare postop with preop metrics, but also with our entire patient database. VR12 is a short form based on the Veterans SF36 version, has 2 domains and 8 dimensions leading to 12 questions, and generates two aggregate summary scores (Physical Component & Mental Component summaries), which are standardized using weights derived from the general population survey and calibrated so that 0.50 is the threshold defining the status of the respondent. Washington University has standing approval ([name]) to use the VR12 and scoring algorithm. The Barthel questionnaire assesses functional independence (able to complete 10 specific normal activities like bathing, feeding, dressing, with any help). It generates a weighted aggregate score 0-100 (100=highest independence). We will evaluate patients' return to employment (defined as work for pay or volunteer work outside home). If applicable, specific questions targeting the reason (pain, addiction, etc) for not returning to work will be asked at 30d, 6mo and 1yr.

Throughout the investigation, any adverse events will be described, recorded and reported according to GCP and IRB regulations.

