### 2.6.8 Primary and secondary outcome measures

Primary outcome measure: Total 30d post-discharge home opioid use (number of tablets). This is because surgeons prescribe a variety of post-op opioids (oxycodone, tramadol, oxycodone+acetaminophen, hydrocodone+acetaminophen, codeine+acetaminophen), we avoid any confounding by use of opioid conversion tables, and the most important factor in opioid diversion and misuse is the number of left-over tablets.

Secondary outcome measures:

1. Total 7d post-discharge home opioid use (number of tablets).
2. Total intraoperative non-methadone opioid administration
3. Total PACU opioid administration
4. Total hospital non-methadone opioid administration

Exploratory outcomes:

1. Total day of surgery nonmethadone IV opioid administration
2. Total day of surgery nonmethadone IV and oral opioid administration
3. Total day of surgery opioid administration
4. Postoperative day 1 total IV oral and opioid administration (for short-stay cohort only)
5. Total hospital opioid administration
6. PACU pain scores (NRS) and pain relief score; at time-specific intervals
7. Duration of intraoperative analgesia (median time to request for re-medication with opioid)
8. PACU side effects and adverse events: respiratory depression (4 events occurrence per above), sedation (MOAA/S score), nausea/vomiting (number of events); at time-specific intervals and total
9. PACU duration of stay
10. 7d and 30d total post-discharge home opioid use (in morphine equivalents)
11. 7d and 30d post-discharge pain scores (NRS) and pain relief score; daily
12. Total pain relief (TOTPAR), calculated as the area under the curve of pain relief score vs time
13. 7d and 30d post-discharge opioid side effects (ORSDS); daily, weekly and total (summed and average)
14. Time to cessation of post-discharge opioid use
15. 7d and 30d post-discharge unused opioid tablet count
16. Quality of recovery at 7d, 14d, 21s, 30d, 6 mo, and/or 12 mo (VR-12, Barthel index, QoR-15, functional independence, return to work)
17. Surgeons' opioid prescribing patterns

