### 2.8 Hypothesis testing

For all Aims, the two cohorts ("short-stay" and "same-day" surgery) are analyzed separately. Subgroup analysis may also explore specific surgical procedures (procedure-specific analgesia).

Aim 1: Compare the influence of methadone vs short-duration opioids on short-term (before discharge) and intermediate term (1-30d post-discharge) opioid consumption.

30d post-discharge opioid use ( $> 5$  pills) will be compared between arms using Chi-square tests and multiple logistic regression, with opioid group as a predictor and adjusting for the important clinical and demographic covariates. Total pill consumption will be compared using GEE model with Poisson link function. In addition, a time-to-event (survival) model will be fit to compare time to opioid discontinuation between the two groups.

adjusting for the appropriate covariates. Opioid use during intraop, in-hospital post-op, and post-discharge periods will be evaluated using appropriate model and data transformation, depending on the distribution of the data. It is common in some analgesic trials that subjects dropping from different treatment groups differ with respect to reasons for early discontinuation (i.e. not random but outcome-related). Therefore analysis will not be “completers only”. Drop-out rates will be compared between the drug groups, and 30d opioid consumption ( $>5$  vs  $\leq 5$  pills) analyzed with and without drop-outs. Drop-outs will be censored at the time of dropping out in time to discontinuation analysis. A corollary of opioid consumption by patients is opioid prescribing by surgeons. It is possible that surgeons’ prescribing practices (# tablets per patient) may change during the study (coincidentally or as a result thereof) and this will be explored.

**Aim 2:** Compare methadone vs short-duration opioids in reducing short-term (immediate postoperative), intermediate term (1-30d post-discharge), and chronic (6-12 mo) postoperative pain.

Pain reduction effectiveness of methadone vs short-duration opioids will be compared using repeated measures models to adjust for multiple measures on each subject. Depending on the distribution of NRS, VAS and pain relief data, data will be analyzed as normal, or transformed into an ordinal or other scale.

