#### **4.4 Procedures to Minimize Potential Risks**

a. Recruitment and Informed Consent. The study will be conducted under appropriate Duke University IRB protocol and consent form approvals. The study will be conducted under the supervision of the PI, who is a Board-Certified anesthesiologist with decades of experience in the conduct of human volunteer studies, and Co-Investigators, who are Board-Certified Anesthesiologists or Surgeons. Potential subjects will be approached in the pre-operative assessment clinic, or identified through IRB-approved review of the surgical schedule prior to their surgery, at which time they will be contacted and asked if they are interested in participating. An IRB-approved phone screen will be conducted and a consent visit scheduled in advance of surgery for subjects that wish to participate. This visit may also occur on day of surgery when allowing sufficient time for explanations, questions and answers. If interested and willing, subjects might also be fully consented using IRB approved eICF. All enrolled subjects must provide informed consent, evidenced by signing an informed consent document.

b. Protections against Risk.

i) Eligibility criteria exclude patients with known renal or hepatic disease, which may affect opioid disposition, as well as pregnant or nursing females. Patients with known history of hypersensitivity to opioids or, conversely, are opioid tolerant (e.g. preoperative methadone therapy or use of fentanyl or buprenorphine transdermal patches) are also excluded. For safety reasons, children and patients older than 65 yr are not studied, because of declining methadone elimination and increased risk of respiratory depression with age.

ii) Methadone dosing is fixed, using ideal body weight, rather than actual body weight, to obviate risk of excessive dosing due to obesity. The investigational pharmacist will be unblinded.

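### Preoperative opioid use is not a named covariate or stratum for the 30-day tablet outcome, although the listed exclusion does not clearly keep out patients taking one or two opioid pills a day

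*Combined protocol and SAP*

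**What the plan says.** The Exclusion Criteria (section 2.5, repeated in the Synopsis) rule out "Chronic opioid use (e.g. preoperative daily use of methadone, buprenorphine, fentanyl transdermal patches" and, as the last example, 3 or more oxycodone pills. This is the only numeric opioid limit, and it sits in an illustrative list. Section 4.4 adds that patients who "are opioid tolerant (e.g. preoperative methadone therapy or use of fentanyl or buprenorphine transdermal patches) are also excluded", again by example and without mention of low-dose oral use.

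Section 2.6.8 gives the endpoint: "Primary outcome measure: Total 30d post-discharge home opioid use (number of tablets"). No subtraction of preoperative intake is described. Section 2.6.7 takes use from the monitoring system, the daily questionnaire "and residual pill counts, and recorded both as the number of tablets used and total morphine equivalents". It has no rule for tablets from a supply that the patient already held.

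In section 2.7, "an ideal state of post-discharge opioid use is defined as" at most 5 pills in 30 days. The rate above that, in the preliminary data, "was 45% in the short-duration opioid group". Section 2.2 says the pilot studies had the same eligibility criteria as this trial.

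For Aim 1, section 2.8 plans chi-square tests and a multiple logistic regression "adjusting for the important clinical and demographic covariates", which are not listed. The GEE/Poisson model for total pills is given with no covariates. Section 2.6.2 names no stratification factor beyond cohort. Section 2.6.3 states: "Patient information (demographics, medical history, procedure, medications, pain scores) will be extracted" from the electronic record.

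**The concern.** A low-dose daily user who keeps taking the same number of pills would pass the 5-pill cut-off soon after discharge, whichever intraoperative opioid was given. Such a patient tells us little about treatment in the binary analysis and can add a large number of tablets to the total. Preoperative use is therefore likely to be a strong predictor of the primary outcome, and it can be derived from data already being collected.

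As written, the chi-square test cannot use it, the tablet-count model does not mention it, and the logistic model may or may not include it. What is at stake is precision and the clarity of the prespecified analysis. Randomization still protects the comparison from systematic bias.

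**Working it through.** **Inputs.** High-use rate 45% in the short-duration arm, relative risk 0.65, 150 per arm, alpha 0.05 (section 2.7). Sidedness is not stated; two-sided is assumed. The share *f* of enrolled patients taking one or two pills a day before surgery is not in the documents. It is an assumption, shown over a range.

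**Pill arithmetic.** 1 × 30 = 30 and 2 × 30 = 60 tablets. More than 5 is reached on day 6 at one a day and on day 3 at two a day.

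**The plan's own figure.** The methadone-arm rate is 0.65 × 0.45 = 0.2925. Power of the pooled chi-square test is Φ{[d − 1.96√(2p̄q̄/n)] / √[(p₁q₁ + p₂q₂)/n]}. With d = 0.1575, p̄ = 0.37125 and n = 150, this is Φ{(0.1575 − 0.1093)/0.0550} = 80.9%. For 80% power, 147 per arm are needed. The stated 150 per group reproduces. With the rounded 30% that the section also prints, 163 per arm are needed and power at 150 is 76.8%; the comparisons below use 0.2925.

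**What the planning rates might describe.** Take baseline users as high in both arms. The documents allow three readings.

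- A: 45% and 0.65 describe non-users only. Mixed rate = f + (1 − f)p. At f = 5%: 0.05 + 0.95 × 0.45 = 0.4775 and 0.05 + 0.95 × 0.2925 = 0.3279.
- B: 45% already includes users, and 0.65 applies to non-users. At f = 5% the non-user control rate is (0.45 − 0.05)/0.95 = 0.4211, the treated rate is 0.65 × 0.4211 = 0.2737, and the mixed treated rate is 0.05 + 0.95 × 0.2737 = 0.310.
- C: 45% and 29.25% both already describe the eligible mix. At f = 5% the non-user rates are 0.4211 and (0.2925 − 0.05)/0.95 = 0.2553.

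**Accounting for baseline use** is approximated by a stratified test. The always-high stratum adds no information, so n per arm is 150(1 − f) at the non-user rates.

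| f | A: unadjusted → accounted for | B | C |
|---|---|---|---|
| 2% | 78.8% → 80.1% | 77.1% → 78.5% | 80.9% → 82.3% |
| 5% | 75.5% → 78.9% | 70.7% → 74.6% | 80.9% → 84.5% |
| 10% | 69.9% → 76.7% | 58.6% → 67.0% | 80.9% → 88.4% |

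At 1%, reading A goes from 79.9% to 80.5%. The gain at 5% is 3.4, 3.9 and about 3.6 points. At 1 to 2% it is about 1 point.

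**Tablet total.** At f = 5%, 15 of 300 patients are baseline users, and the between-arm difference in their number has an SD of about √15 ≈ 4. Four extra users at 30 to 60 tablets move an arm's mean by 4 × 30/150 = 0.8 to 4 × 60/150 = 1.6 tablets per patient, before deducting what the patients they displace would have taken. At f = 2% (6 users, √6 ≈ 2.4) the shift is about 0.5 to 1.0. The documents give no mean or SD for tablets, so this cannot be turned into power.

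**The case against.** Much of the case on the other side stands.

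- *Eligibility.* A reader might infer that one or two pills a day is plainly allowed. The list is illustrative and sits under chronic use, so an investigator could exclude such a patient. The text does not settle it.
- *Outcome fixed at entry.* A reader might also infer that these patients are high users whatever happens. That needs intake to continue for 3 to 6 days after discharge and the tablets to be counted. Neither is stated. If tablets from an old supply are missed, they do not push anyone over 5. The daily questionnaire could capture them, but no rule says whether they count.
- *Power loss against plan.* It is tempting to read the fall to 75.5% or 69.9% as a shortfall in the trial. The pilot had identical criteria, so the 45% may already contain such patients. Under reading C nothing is lost against plan; under B the loss is larger than under A. The documents do not say which applies.
- *Modelling as a cure.* Under A and B it recovers only part of the loss, because patients who are high in both arms carry no information on treatment. If all of them are high, an ordinary logistic term separates.
- *Already covered.* The logistic model adjusts for important clinical covariates, and preoperative opioid use might be one. But an unnamed covariate is not prespecified, and that phrase reaches neither the chi-square test nor the count model.

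These points limit the size of the problem. They do not remove the case for naming the variable, since accounting for it raises power under all three readings.

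**Conclusion.** The point holds as a recommended improvement to the primary-outcome analysis, not as a demonstrated flaw in the sample size. The listed threshold does not clearly exclude low-dose daily users, their continued intake would exceed the cut-off, and no primary-outcome analysis names preoperative opioid use although the data are collected.

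Its size depends on an unknown share. At an assumed 5%, accounting for baseline use is worth about 3 to 4 power points; at 1 to 2%, about 1 point. These figures assume that baseline users are all high in both arms, a two-sided test, 150 evaluable per arm, and the stratified approximation. If only some continue their intake, the figures change.

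**What to change.** From the medication list already extracted, derive preoperative opioid use as none versus any, and as tablets per day. In section 2.8:

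1. Prespecify it as a covariate in the GEE/Poisson tablet-count model.
2. For the >5-pill outcome, prespecify it as a stratum in a stratified test or as a covariate in the logistic model, with a penalised fit if there is separation.
3. Add a sensitivity analysis that omits baseline users.
4. State, with section 2.6.7, whether tablets from a preoperative supply count toward the total.

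The primary outcome and eligibility stay unchanged. Counting only tablets above the preoperative number would be a different outcome from the one in section 2.6.8, so it is not proposed here.

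The cost is one derived baseline field and some wording. No visits or patients are added. The sensitivity set is slightly smaller, for example about 285 instead of 300 per cohort if 5% are baseline users (300 × 0.95).
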